#### **All Patients**

The all patients population will include any patient who was assigned a patient screening number, whether subsequently randomized or not.

This population will be used in summarizing the patients who participated in the screening period regarding their patient disposition, baseline characteristics in summary tables and listings

#### **Data Points Requiring Special Handling**

For ITT analysis, patients with multiple assessments within a scheduled visit will be included by selecting the first assessment in time within a visit. However, all data will be presented in the patient data listing.

### **Sub-Group Analyses**

The primary and key secondary efficacy variables (i.e., COWS score, VAS pain and craving scale) and neurocognitive assessment will be summarized for the following sub-groups:

- Sham or active group
- Demographic groupings including gender age and type of opioid medication abused.

### Patient disposition and analysis population

The number of patients enrolled will be summarized by treatment group, and a patient listing of all patients excluded from each of the analysis populations will be generated.

### **Baseline characteristics**

Summary statistics will be presented for each treatment group for the following demographics and baseline characteristics: gender, age, race, weight, height, and body mass index (BMI), evaluations done.

### **Efficacy Analysis**

All efficacy data will be analyzed using the ITT patient population. In addition, key efficacy analyses will be repeated using the mITT population.

Results of the COWS and pain VAS scores, OCS and CNSVS assessments at the respective time points will be tabulated and analyzed. In addition, other variables of interest below will be tabulated:

• Percent reduction in COWS, VAS for pain and craving for each patient will be calculated as percentage of baseline.

• Percent less than a three for VAS by day

- Percent of subjects needing rescue medication over first 5 days.
- Percent of subjects who achieve a COS less than 10 in the first hour, at end of first day
- Dose of buprenorphine at first day and total over first 5 days.

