#### **DESIGN AND METHODS**

The study will recruit a total of 50 subjects and will take place in a well-established outpatient treatment center (Brightview). Brightview is a private addiction treatment center located in Cincinnati, Ohio. The site PI at Brightview will be [name] [name] (MD, ABIM, ABAM DABPM), a board-certified physician in addiction medicine. [name] (PhD) will be a Co-investigator. The volume of patients treated for opioid use disorder (OUD) at this facility is sufficient for patient recruitment in this study. [name] will be responsible for patient recruitment and overseeing the entire project at Brightview. He will monitor the health of all patients in the study per standard clinical practice. [name] will be responsible for patient recruitment as well and monitor protocol adherence as well as supervise data collection, entry, and analysis.

This study will involve a double-blind, randomized, controlled trial with active BRIDGE or sham device (Figure 3). The sham device will be identical in appearance to the active device but will have no electrical current. Both providers and patients will be blinded to treatment allocation throughout the study. Participants will be 18 years or older who speak English and meet criteria for opioid use disorder based on the Diagnostic and Statistical Manual of Mental Disorders-5. Patients going through acute opioid withdrawal will be assessed for the severity of opioid withdrawal using the Clinical Opioid Withdrawal Scale (COWS). Additional demographic data will be collected at presentation including age, sex, duration of opioid misuse, types of medications or illicit drugs used as well as the presence of other medical conditions. After the severity of opioid withdrawal is established (COWS score  $\geq 10$ ), subjects will be randomized in blinded fashion. Once the patient is consented, a visual analog scale (VAS) for pain and an opioid craving scale (OCS) will be completed. Baseline cognitive function will be measured with the Stroop test using the CNS Vital Signs (CNSVS) in-office neurocognitive testing software https://www.cnsvs.com/index.html. This instrument measures executive function. The test takes approximately

4 minutes to administer and will be performed at the same intervals as COWS score, pain and craving assessments before and after device placement.

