Participants in this study will be males and females between the ages of 18 and 60 years who are English speaking and capable of giving informed consent. Applicants must fulfill the criteria for opioid use disorder based upon the Structured Clinical Interview for DSM-5 (SCID). In addition, they must have an opioid (morphine, 6MAM, oxycodone or metabolites, hydrocodone or metabolites or fentanyl or metabolites, methadone or metabolites) positive urine immunoassay test during the screening process and have evidence of opioid withdrawal with COWS score  $\geq 10$ . They must be healthy, with no significant medical illnesses (e.g., insulin dependent diabetes), and without significant psychiatric illness (e.g., schizophrenia) other than their drug dependence.

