#### Exclusion criteria

Subjects will be excluded if they have other serious medical or psychiatric disorders or if they have a codependence on other substances such as alcohol or benzodiazepines. Patients who test positive for benzodiazepines will be excluded. They will also be excluded if they are suicidal or homicidal. Women will be excluded from entering the study if they are pregnant.

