#### **Demographic Information**

Data will be collected as part of the clinic visit. This includes subject's date of birth, age, sex and ethnicity. The physician assessment will also include questions about prior medical diagnoses, co-morbid symptoms and the characteristics of the current illness. Types of illicit drugs used other than opioids (benzos, alcohol, etc.), duration of drug use, underlying psychiatric disorders.

Efficacy Information

- 1. Clinical Opioid Withdrawal Scale (COWS) (total time 5 min)
- 2. Pain (11-point VAS) (total time 2 min)
- 3. Opioid Craving Scale (11-point scale) (total time 3 min)

a. How much do you currently crave opiates (Range: 0-10, 0 = not at all, 10 = extremely)

b. In the past week, please rate how strong your desire to use opiates has been when something in the environment has reminded you of opiates (examples: seeing a medication bottle, using the Internet, visiting a doctor's office, going to a place where you used to buy drugs)? (Range: 0-10, 0 = not at all, 10 = extremely)

c. Please imagine yourself in the environment in which you previously used opiates (examples: a party, a hangout, a particular room where you live). If you were in this environment today and if it were the time

of day that you typically used opiates, what is the likelihood that you would use opiates today? (Range: 0-10, 0 = not at all, 10 = extremely)

- 4. CNS Vital Signs in-office neurocognitive testing with domain scores (total time 15 min). https://www.cnsvs.com/index.html
- 5. Four question patient questionnaires at end of study period
- 6. Dosing of medication assisted therapy (buprenorphine)
- 7. Additional (symptom control) medication log
- 8. Number of subjects with continued engagement in recovery treatment at 5 days post-device placement
- 9. Whether the patient thinks they had an active or inactive device at end of 5 days treatment

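### Per-patient percent reduction is undefined at zero and unstable at 1 or 2 for pain and craving, because entry sets a minimum only for COWS

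*Combined protocol and SAP*

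**What the plan says.** Efficacy Analysis lists several variables in addition to the scores themselves, introduced with "other variables of interest below will be tabulated". Two matter here:

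- The first is a ratio to each patient's own starting value: "Percent reduction in COWS, VAS for pain and craving for each patient will be calculated as percentage of baseline".
- The second is a daily threshold count, worded as "Percent less than a three for VAS by day".

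Neither carries a condition on the baseline value, and the first has no rule for a zero denominator. Data Points Requiring Special Handling and Missing data do not supply one.

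The inclusion paragraph under Data Management requires that patients "have evidence of opioid withdrawal with COWS score" of at least 10. That is the only symptom-score minimum; the Exclusion criteria add none for pain or craving. According to Design and Methods, after consent "a visual analog scale (VAS) for pain and an opioid craving scale (OCS) will be completed", again with no threshold.

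The scales are listed under Demographic Information. Pain is given as "Pain (11-point VAS) (total time 2 min" without its end points written out. Craving has three items, each scored 0 to 10, the first being "How much do you currently crave opiates (Range: 0-10, 0 = not at all, 10 = extremely". No rule for combining the three is stated.

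The analysis-population section makes the ITT set, meaning every randomized subject, primary for all efficacy analyses.

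**The concern.** A ratio to baseline behaves well only when the baseline is kept away from zero. The entry rule does that for COWS and for nothing else. A patient can reach a COWS of 10 through signs such as pupil size, yawning, tremor or heart rate and still report little pain.

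Three things follow for pain and craving. A patient with a zero baseline has no percent reduction, although both scores were observed, so this is not missing data in the sense of the Missing data section. A patient who starts at 1 or 2 can produce a very large value from a small change. And the plan leaves open whether an undefined value is dropped, set to zero or imputed, so the choice could be made after results are known. Pain and craving are Aim 2 outcomes, and the Background presents the earlier device results as percent reductions, so readers are likely to look at these tables.

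**Working it through.** **Inputs.** 50 patients, 25 per arm (Power Calculation); COWS at least 10 at entry; each craving item 0 to 10; pain on an 11-point scale, taken as 0 to 10 (assumption). The documents give no baseline distribution for pain or craving.

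**1. The plan's own figure.** The only stated figure nearby is at least 90% power for the primary COWS comparison. With 25 per arm, a difference of 0.94 SD and two-sided alpha 0.049, the noncentral t has 48 degrees of freedom and noncentrality 0.94 × √(25/2) = 3.32, giving 90.1%. It reproduces, and nothing below alters it.

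**2. Percent reduction = 100 × (baseline − follow-up) / baseline.**

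| Baseline | Follow-up | Absolute reduction | Percent reduction |
|---|---|---|---|
| 0 | any | 0 or negative | undefined |
| 1 | 0 | 1 | +100% |
| 1 | 2 | −1 | −100% |
| 1 | 3 | −2 | −200% |
| 2 | 1 | 1 | +50% |
| 8 | 7 | 1 | +12.5% |
| 8 | 4 | 4 | +50% |

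A one-point improvement is worth 100, 50 or 12.5 points depending only on where the patient began. For COWS, with a baseline of at least 10, one point is never worth more than 1/10 = 10 points.

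**3. Effect on an arm mean.** One patient going from 1 to 3 contributes −200/25 = −8 percentage points relative to no change; from 1 to 2, −100/25 = −4 points.

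**4. Chance of at least one undefined value.** With a zero-baseline share p, assumed the same and independent across patients, the chance is 1 − (1 − p)^50.

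| p (assumed) | Expected patients, 50p | Chance of at least one |
|---|---|---|
| 2% | 1 | 64% |
| 5% | 2.5 | 92% |
| 10% | 5 | 99% |

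**5. The below-three count.** Let q be the share of each arm below three at baseline, and suppose none of them rises to three or more. With conversion rate c among the rest, the observed share is q + (1 − q)c. Taking q = 20% and c = 25% on sham and 60% on active (all assumed):

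- sham: 0.20 + 0.80 × 0.25 = 40%
- active: 0.20 + 0.80 × 0.60 = 68%

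The difference is 28 points instead of 35, a shrinkage by the factor 1 − q. The chance difference in q between two arms of 25 has SD √(2 × 0.2 × 0.8/25) = 11.3 points.

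**The case against.** The strongest reply is that little depends on these tables. They are extras with no test or alpha attached. The same section already tabulates and analyzes the pain and craving scores at each time point. The secondary MMRM takes baseline score and baseline-by-visit as effects and reports adjusted differences with confidence intervals. The General Considerations call for median, minimum and maximum as well as the mean, so an extreme value would be visible. The Background describes pain as common in acute withdrawal, and COWS itself includes muscle aches and craving, so zero baselines may be rare. If the three craving items are summed or averaged, a zero needs all three at zero. All of this stands and limits the size of the point. It does not remove it: a median does not help with a value that cannot be computed.

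A reader might go further and infer that anyone entering below three is a guaranteed success in the VAS count, so that the count is biased and should be confined to patients starting at three or above. The documents do not support that. A patient who enters at 1 can rise to 3 and then no longer counts. The line can be read as a description of how many patients have low scores each day, which is legitimate for all patients. Randomization balances the baseline mix in expectation, leaving dilution and chance imbalance but no systematic bias. Restricting the set would depart from the ITT population and hide worsening among patients who began low. The line also does not name its scale: elsewhere VAS is mostly paired with pain and OCS with craving, so its application to craving is uncertain.

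**Conclusion.** The point holds for per-patient percent reduction in pain and craving. As written, the measure is undefined at a baseline of zero, which removes patients from a table meant to cover everyone randomized, and unstable at 1 or 2, where a single patient can move an arm mean by 4 to 8 points in the examples above. COWS percent reduction is protected by the entry minimum.

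How often this occurs cannot be established from the documents; the 64% to 99% range rests on assumed zero shares of 2% to 10% and on a 0-to-10 pain scale. For the below-three count, what survives is a need to name the scale and show the baseline proportion. The consequence is limited to descriptive tables, so this is a minor improvement: the primary comparison, its power and the repeated-measures analysis are unaffected.

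**What to change.** In Efficacy Analysis, keep per-patient percent reduction for COWS only. For pain and craving, tabulate absolute change from baseline, which matches the change-over-time analysis in the MMRM, and state how the three craving items are combined or that they are shown separately.

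For the below-three line, keep all ITT patients, name the scale, and print the proportion below three at baseline beside the daily figures. The subset starting at three or above can be shown as well, with its denominator (about 20 per arm if 20% start below three), but as an addition and not a replacement.

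The cost is a few sentences, best settled before unblinding. The downside is that percent reductions in pain and craving would no longer be available to set beside the percent figures quoted for COWS. Sample size does not change.

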#### **Primary Efficacy Variable**

The primary efficacy variable is change in COWS from baseline to first hour. The two groups will be compared using a two-sided two sample t-test at an alpha of 0.001 at an interim analysis of the first 24 completing and at an alpha of 0.049 after 50 have completed.

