#### DATA MANAGEMENT

Subjects will be randomized in a 1:1 ratio to receive either active or a sham device. Randomization in blocks of 10 (5 for each treatment) will be determined using the computer program randomization.

The severity of opioid withdrawal signs and symptoms will be assessed with the COWS at several time points: 1) pre-device placement, 2) 1-hour post placement of sham or active device, 3) two hours post placement (approximately one hour after first dose of buprenorphine), 4) at subsequent follow-up in clinic on day 2 and 5) at final follow-up in clinic on day 5 prior to removal of device. The visual analogue pain and craving scale will also be administered at intervals to monitor patient comfort: 1) pre-device placement, 2) 1-hour post placement of sham or active device, 3) two hours post placement (approximately one hour after first dose of buprenorphine),4) at subsequent follow-up in clinic on day 2, 5) in clinic or remotely (via phone) on days 3 and 4, and 6) at final follow-up in clinic on day 5 prior to removal of device. Assessment of cognitive function (CNSVS) will be recorded at 1) pre-device placement, 2) 1-hour post placement of sham or active device, and 5) at final follow-up in clinic on day 5 prior to removal of device. One hour following placement of either sham or active device, the patients will be given the first dose of buprenorphine with a starting dose of 2, 4 or 8 mg at the blinded provider's discretion based on BMI, patient previous experience with BUP, patient apprehension or other factors. Adjustments to this dose will not be made for at least an hour after receiving the first dose but the providing clinician may order additional buprenorphine after one hour as indicated by initial response, previous experience, presence of precipitated clinical opioid withdrawal scale (COWS) and BMI. Subsequent adjustments will be made based on the blinded provider's discretion and patient needs and comfort as per clinic standard. Ancillary (supportive) medications to help manage signs and symptoms of opioid withdrawal will NOT be allowed for one hour after the first dose of buprenorphine. Following the first hour, symptom control medications including ibuprofen, clonidine, ondansetron, loperamide, and acetaminophen may be furnished or prescribed. A medication log will be provided to track usage of this modality. Subjects will remain blinded and keep the device on for 5 days regardless of randomization status. Subjects will be asked to return to clinic for additional induction visits based on the clinic standard of care which will be Day 2 and in some cases Days 3 & 4. In order to monitor whether neurostimulation with the BRIDGE has any added benefit for patients on outpatient opioid agonist therapy, subjects (regardless of active or placebo) will be reassessed using OCS and VAS at each subsequent visit, or remotely (via phone) when unrequired to return to clinic, during the 5-day trial.

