#### Secondary efficacy analysis

As a secondary analysis we will examine the change over time of the COWS, pain VAS scores, OCS and CNSVS between groups using a mixed-effects model repeated measures (MMRM) analysis incorporating treatment period data up to 3 months. The effects in the model will include the baseline score, treatment groups, visit, treatment-by-visit interaction and baseline-by-visit interaction. Visit week will be treated as the repeated variable within a patient. Patient, treatment, and visit will be treated as class variables. Unstructured covariance matrix will be used initially, and additional types (e.g., auto- regression, Toeplitz, CS, etc.) will be tried to assess the robustness of the unstructured matrix. Comparison between treatments will be based on contrasts of least square treatment means at each week of interest. Based on the analysis above, least square means, standard errors, and 95% confidence intervals (CI) of treatment difference will be reported for the two groups.

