#### Power Calculation for primary aim (difference in COWS scores between active and sham device).

We hypothesize that compared to sham treatment, the improvement in COWS due to the BRIDGE device will be significantly higher than the sham. Similarly, pain and craving as measured by the VAS and OCS will be reduced. Patients with the active BRIDGE device will have improved memory and executive function compared to sham as assessed by CNSVS.

The primary outcome is comparison of change from baseline of the COWS scores between active and sham device at one hour. The data will be analyzed as a randomized, placebo-controlled trial with an interim analysis when 24 patients are completed at a P< 0.001. We will compare the bridge device and sham using a two sided t-test of the change of COWS at one hour form baseline. Using the sample size software Pass 15 with 25 subjects in each group we will have at least 90% power at an alpha of 0.049 to detect a difference in the COWS at one hour between treatment and sham of at least .94 standard deviations(SD), In the withdrawal study we had a SD of ~6, and so if we have a similar variability we will be able to detect a difference of approximately 5.7 (1). In the paper, we found a difference of > 12, so even allowing for a placebo effect we should have adequate power.

Period	Baseline	(1-hour after BRIDGE)	(1-hour after BUP)	Post- MAT	Post- MAT	Post- MAT	Post- MAT
Contact	Clinic	Clinic	Clinic	Phone	Phone	Phone	Clinic
Project Day	1	1	1	2	3	4	5
Informed Consent	Х						
Demographics and Medical History	Х						
Prior and Concomitant Medications	Х						х
Vital Signs, height, weight and BMI	х						
Physical Examination	Х						
Placement of BRIDGE Device or sham	Х						
COWS scores	Х	х	Х	х			х
VAS pain and craving scale	Х	х	Х	Х	х	Х	Х
Neurocognitive assessment	Х	x					Х
First dose of Buprenorphine		Х					

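### The primary t-test on one-hour change in COWS is valid but leaves out pre-device COWS; adding it as a covariate would probably raise power at the planned effect size

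*Combined protocol and SAP*

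**What the plan says.** Under Primary Efficacy Variable, "The primary efficacy variable is change in COWS from baseline to first hour". The analysis follows: "The two groups will be compared using a two-sided two sample t-test at an alpha of 0.001 at an interim analysis" of the first 24 completers, then "at an alpha of 0.049 after 50 have completed". The Power Calculation section agrees: "We will compare the bridge device and sham using a two sided t-test of the change of COWS at one hour form baseline". Neither section names a covariate. The sample size rests on 25 per group, alpha 0.049, at least 90% power and a difference of 0.94 SD. With an SD of about 6 taken from the earlier uncontrolled study, "if we have a similar variability we will be able to detect a difference of approximately 5.7" COWS points.

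The covariate is available. Under Data Management, withdrawal severity "will be assessed with the COWS at several time points: 1) pre-device placement, 2) 1-hour post placement". Baseline COWS also decides entry: participants must "have evidence of opioid withdrawal with COWS score" of at least 10.

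The plan adjusts for baseline in one place, the mixed model under Secondary efficacy analysis: "The effects in the model will include the baseline score, treatment groups, visit, treatment-by-visit interaction and baseline-by-visit interaction". That model treats visit week as the repeated variable and places its treatment contrasts at weeks of interest. It names no one-hour contrast.

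**The concern.** Analysing change from baseline amounts to fixing the slope of one-hour COWS on pre-device COWS at 1. If the true slope is different, part of the baseline variation stays in the error term and the treatment effect is estimated less precisely than the same data allow. ANCOVA estimates the slope, so it removes that variation and also corrects for chance baseline imbalance between arms.

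The stake is power in a small trial: 25 per arm at the final look and, assuming an even split, 12 per arm at an interim tested at 0.001. The design sits close to 90% power at its own planning difference, so there is little reserve if the sham-controlled effect is near that figure. The plan itself allows that a placebo effect may shrink the difference seen earlier. Validity is not in question.

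**Working it through.** **Inputs from the documents.** n = 25 per arm at the final look; 24 completers at the interim (12 per arm assumed); two-sided alpha 0.001 and 0.049; difference d = 0.94 SD; SD about 6. The plan does not say whether this SD belongs to the change or to the one-hour score. I take it as the SD of change, the scale that is tested. **Not in the documents:** the baseline to one-hour correlation (rho) and the ratio of the two SDs, so ranges are shown.

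**1. The plan's own figure.** Two-sample t, df = 48, noncentrality 0.94 × √(25/2) = 3.32, alpha 0.049: power **90.1%**. The stated 90% reproduces. In points, 0.94 × 6 = 5.64, consistent with the plan's approximate 5.7. The alphas sum to 0.001 + 0.049 = 0.05.

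**2. ANCOVA formula.** With baseline SD s0 and one-hour SD s1, the ratio of ANCOVA error variance to change-score variance is

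s1²(1 − rho²) / (s0² + s1² − 2·rho·s0·s1).

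For equal SDs this is (1 + rho)/2: 0.65, 0.75, 0.85 and 0.95 at rho 0.3, 0.5, 0.7 and 0.9. It equals 1 when the slope rho·s1/s0 is 1. Power uses df = 2n − 3 and is averaged over chance baseline imbalance (variance inflation 1 + F/(2n − 2), with F on 1 and 2n − 2 df).

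**3. Final look, d = 0.94, alpha 0.049 (t-test 90.1%).**

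| s1/s0 | rho 0.3 | 0.5 | 0.7 | 0.9 |
|---|---|---|---|---|
| 1 | 97.8% | 96.0% | 93.6% | 90.9% |
| 1.25 | 95.2% | 92.5% | 90.0% | 90.9% |
| 1.5 | 93.1% | 90.5% | 89.5% | 95.4% |

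At a slope of exactly 1, power is 89.4%, a loss of 90.1 − 89.4 = 0.7 points.

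**4. Difference detectable with 90% power, SD of change 6.** t-test 5.6 points; ANCOVA with equal SDs 4.6, 4.9, 5.3 and 5.6 at the same four correlations; 5.7 at slope 1.

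**5. Interim look, 12 per arm, alpha 0.001, equal SDs.**

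| Effect | t-test | rho 0.3 | 0.5 | 0.7 | 0.9 | slope 1 |
|---|---|---|---|---|---|---|
| 0.94 SD | 10.4% | 19.9% | 15.6% | 12.5% | 10.3% | 9.4% |
| 2 SD (12/6) | 84.1% | 96.7% | 93.2% | 88.7% | 83.5% | 80.8% |

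**6. A case built on figures in the documents.** The background table of buprenorphine induction gives pre-dose SDs of about 3.5, in a different population and under a different treatment. With baseline SD 3.5 and SD of change 6, the variance ratio is 1 − ((1 − slope) × 3.5/6)².

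| Slope | Variance ratio | Final, 0.94 SD | Interim, 2 SD |
|---|---|---|---|
| 0.3 | 0.833 | 94.0% | 89.5% |
| 0.5 | 0.915 | 91.9% | 85.4% |
| 0.7 | 0.969 | 90.3% | 82.5% |
| 1 | 1 | 89.4% | 80.8% |

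**7. Simulation, final look only** (bivariate normal, equal SDs, 20,000 trials per setting). Power: t-test 90.2–90.4%; ANCOVA 98.0%, 96.0%, 93.8% and 91.0% at the four correlations. Type I error: 4.7–5.0% and 4.8–5.1%, against a nominal 4.9%. The interim figures come from the formula alone.

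**The case against.** The strongest reply is that nothing here is wrong and that the size of the gain is unknown. Both parts are true.

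The equal-SD row also fits the plan's own numbers poorly. With a baseline SD of 3.5, equal SDs and a non-negative correlation, the SD of change cannot exceed 3.5 × √2 = 4.95, which is below 6. Step 6 uses both figures. There the final-look change runs from −0.7 points at slope 1 to +3.9 at slope 0.3 (94.0 − 90.1), less than the equal-SD row suggests at low and middle correlations. The entry threshold of 10 narrows the baseline range and pushes in the same direction. This objection stands as a caution about size. It does not reverse the balance, because the loss at the final look stays below one point.

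Second, the plan expects a larger effect. The earlier study showed a difference above 12 points, about 2 SD, where final-look power exceeds 99.9% under either test. What is left is the interim look, and with the step 6 inputs ANCOVA there gains 1.3 points at slope 0.5 and loses 1.6 at slope 0.7. This also stands. However, that study had no control group, so the difference from sham may be smaller.

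Third, the secondary mixed model could be read as already giving a baseline-adjusted one-hour comparison, since one hour is a scheduled COWS assessment. As written, its contrasts are weekly and no one-hour contrast is named. Even if one were, it would be a secondary result and would not govern either look.

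**Conclusion.** The point holds as an efficiency recommendation. The planned test is valid, its power statement is right, and the two alphas add to 0.05. It leaves unused a covariate that the trial already collects and that the plan already uses in its secondary model.

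At 0.94 SD with 25 per arm, adjustment moves final power from 90.1% to between 89.4% and 97.8% over the settings examined. The inputs closest to the documents' own figures give about 90% to 94% for slopes of 0.7 down to 0.3. A slope below 1 is plausible because the plan describes response in proportional terms (an 87% reduction in the earlier study, and percent of baseline as a tabulated variable), but the documents do not establish it. The conclusion rests on the SD of 6 being that of change, 12 per arm at the interim, approximate normality, and a correlation that the documents do not give.

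**What to change.** Before the interim look, prespecify as the primary analysis at both looks (two-sided alpha 0.001 and 0.049) an ANCOVA with treatment as the factor and pre-device COWS as the covariate. The outcome may be one-hour COWS or its change; the treatment estimate is the same. Keep the two-sample t-test on change as a sensitivity analysis. Amend the matching sentence in the Power Calculation section.

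The sample size can stay. The stated 90% remains approximately right in the worst case (89.4%) and is conservative when the slope is clearly different from 1.

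The cost is one sentence in each of two sections and no new data. Statistically, the price is one degree of freedom plus the allowance for chance baseline imbalance. If the slope is 1, that is about 0.7 points of power at the final look; at the interim it is about 1 point at 0.94 SD (10.4 − 9.4) or about 3 points at 2 SD (84.1 − 80.8).
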